2. If patients meet criteria for treatment failure status, their dose of inhaled corticosteroids will be increased to the dose they were receiving at visit 4 (800 $\mu\text{g}/\text{day}$) delivered by an open-label inhaler. Study inhalers of corticosteroids (or its placebo) will be returned to the clinical center. If they meet the criteria detailed in Section VI, they will be treated with appropriate rescue algorithms for an asthma exacerbation. Study inhalers of salmeterol (or placebo) will be continued unless the physician can document that treatment failure status was causally related to taking this medication. They will continue to participate in the study until its termination (intent-to-treat analysis), but no further reductions in inhaled corticosteroid dose will be attempted during this time period. For safety reasons, all subjects will be seen within one week ($\pm 3\text{d}$) from the day they were categorized as achieving treatment failure status. Following this "safety" visit, subsequent protocol visits will continue in accordance with the visit schedule established at Visit 1 (see SOCS/SLIC MOP for details concerning possible replacement of scheduled protocol visits with treatment failure related visits).

IV. OUTCOME VARIABLES

The primary outcome variable will be the time to treatment failure. It will be evaluated using a Kaplan-Meier survival analysis. Secondary outcome indicators will include comparisons of FEV₁, mean peak flow variability (PM-AM peak flow difference normalized by the average of the AM and PM peak flow), methacholine airway responsiveness following premedication with salmeterol (evaluation of bronchoprotective effect), asthma symptom scores, quality of life, and rescue medication use at visits 5-11 to those obtained at visit 4.

Daily data obtained from post-randomization diary cards will be summarized and analyzed as averages. Because subjects are instructed to withhold their study salmeterol (or placebo) for 12 hours prior to a visit, the affected peak flow values will be excluded.

V. PROTOCOL

A. Subjects

1. **Sample size.** This trial has a target sample size of 150 randomized patients, with 20 in Group A, 65 in Group B, and 65 in Group C. See section X.F for the derivation of this sample size.

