In the event of a "treatment failure" (see section III.F), patients will be instructed to come into the Clinical Center as soon as possible, preferably within 72 hours and ideally within 24 hours, in order to have their condition assessed. At this time, the patient will complete Quality of Life Questionnaires, undergo spirometry, and complete a physical exam with adverse events assessment. If the examining physician feels it is safe for the patient to continue, salmeterol reversibility testing will also be performed. Peak flow measures and rescue inhaler use will be reviewed on the diary cards. Any non-study drugs taken prior

to this visit will be documented. If patients meet criteria for treatment failure status, their dose of inhaled corticosteroids will be increased to the dose they were receiving at visit 4 (800 $\mu\text{g}/\text{day}$) delivered by an open-label inhaler. Study inhalers of corticosteroids (or its placebo) will be returned to the clinical center. Study inhalers of salmeterol (or placebo) will be continued unless the physician can document that treatment failure status was causally related to taking this medication.

If they meet the criteria detailed in Section VI, they will be treated with appropriate rescue algorithms for an asthma exacerbation. Trial salmeterol will be continued during exacerbations unless the treating physician considers it appropriate to suspend such therapy until the exacerbation resolves. Reinstitution of trial salmeterol will occur when the exacerbation has resolved at the discretion of the investigator. A record of all medications, dosages, and frequency of occurrence will be kept during exacerbations (see Section VI for additional information regarding the medical management of significant asthma exacerbations).

They will continue to participate in the study until its termination (intent-to-treat analysis), but no further reductions in inhaled corticosteroid dose will be attempted during this time period. For safety reasons, all subjects will be seen within one week ($\pm 3\text{d}$) from the day they were categorized as achieving treatment failure status. Following this "safety" visit, subsequent protocol visits will continue in accordance with the visit schedule established at Visit 1 (see SOCS/SLIC MOP for details concerning possible replacement of scheduled protocol visits with treatment failure related visits).

F. Protocol In Tabular Form

ICS = Inhaled corticosteroid MDI; AS = Active salmeterol MDI;

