Since less-significant changes in symptoms and/or PEF may precede more severe alterations in asthma stability, a series of rescue algorithms has been developed to address the various clinical presentations that may occur (Section VI 2). Once any of these rescue interventions leads to the administration of oral or parenteral corticosteroids, the patient will also be considered to have developed a significant asthma exacerbation. In addition, if in the opinion of the treating physician, corticosteroid therapy is warranted regardless of any antecedent measurements of pulmonary function (PEF, FEV, etc.), value for symptom score, or frequency of rescue beta agonist use, the patient will be considered to have developed a significant asthma exacerbation. It should be noted that although any patient who has developed a significant asthma exacerbation will also achieve treatment failure status, it is possible that a patient may meet the criteria for treatment failure status even though he/she does not meet the criteria for having developed a significant asthma exacerbation.

The time in which a significant asthma exacerbation develops in relationship to the schedule of the SLIC protocol will affect the manner in which future clinic visits, medication adjustments, and diagnostic studies are scheduled or performed.

- Patients developing significant asthma exacerbations during the run-in period will be removed from the study. Once the exacerbation has resolved, the patient may be considered for re-enrollment, starting again at visit 1 and undergoing randomization into either SOCS or SLIC.
- Significant asthma exacerbations which occur following randomization (double-blind treatment phase) will be recorded and the patient considered a treatment failure. During medical management of the exacerbation, trial salmeterol or placebo will be continued, unless the treating physician considers it appropriate to suspend such therapy until the exacerbation resolves. Reinstitution of trial medications (salmeterol or placebo) will occur when the exacerbation has resolved at the discretion of the investigator.

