Trial triamcinolone or placebo will be stopped during exacerbations, and open label triamcinolone acetonide [400 μg (4 puffs) BID] restarted unless the treating physician considers it appropriate to suspend such therapy until the exacerbation resolves. This reinstatement of triamcinolone will occur when the exacerbation has resolved at the discretion of the investigator. A record of all medications, dosages, and frequency of occurrence will be kept during exacerbations. Additional visits and procedures will be scheduled according to guidelines for treatment failure visits (Section E, Visit Structures).

B. Rescue Algorithms

Rescue algorithms will be applied in cases where postbronchodilator PEF falls \geq 35% below baseline and is not improved to $>$ 65% of reference level within 48 hours after increasing as needed albuterol use. Rescue algorithms are based on recommendations from the NAEP Guidelines for the Diagnosis and Management of Asthma (NHLBI Publication No. 91-3042, 1991). Albuterol and oral prednisone are the principal medications for rescue management, therefore, patients will be instructed in their use for home management and supplies of both will be provided throughout the study. For severe acute episodes of asthma, treatment will be administered according to the best medical judgment of the treating physician.

1) Home Care:

Asthma exacerbations will be recognized by an increase in symptoms and by a corresponding drop in PEF below reference level. Patients will be educated to recognize exacerbations as early as possible to facilitate prompt treatment and to lessen morbidity.

- Patients who recognize increased symptoms and/or a fall in PEF to \leq 65% reference level will use albuterol by MDI, 2-4 puffs every 20 min up to 60 min if needed, and then every 4 hours, or less, if needed. Patients will be instructed to use the as needed inhaler for treatment.
- If the PEF does not increase to $>$ 65% reference level or if symptoms are not improved after the first 60 min of therapy, the patient should contact the investigator, their primary physician or seek care in the emergency department. This sequence of events constitutes a significant asthma exacerbation.
- Failure of albuterol to control or maintain PEF $>$ 65% reference level may necessitate the use of corticosteroids (see below).

2) Physician's Office or Emergency Room Treatment:

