- Patients will be assessed by history, physical examination, and by physiological monitoring including spirometry or PEF. If the patient's PEF or FEV₁ is less than 25% predicted or if the patient shows evidence of altered mental status, cyanosis, labored breathing, or use of accessory muscles, sampling of arterial blood for respiratory gas analysis is indicated, with appropriate action taken depending on the results obtained.
- When treated in the physician's office or the hospital emergency room, patients should initially be given albuterol by nebulization (0.5 cc of 0.5% solution) every 20 min over the first 60 min.
- If the PEF increases to > 65% reference level after the first 60 min, the patient can be discharged to continue treatment at home. Prednisone may be administered at the discretion of the physician to augment therapy (see VIF).
- If symptoms persist and PEF remains < 65% reference level, nebulized albuterol should be continued as often as every hour and further treatment with oral or parenteral corticosteroids should be considered (prednisone, 60 mg orally; methylprednisolone, 60 mg iv bolus). Monitoring of PEF or spirometry should continue every hour. Within 4 hours of treatment, a decision should be made regarding patient disposition.
- If PEF increases to > 65% reference level within 4 hours, the patient can be discharged to continue treatment at home. Home treatment should include an 8-day course of prednisone (VI.2.c).
- If PEF remains > 40% but < 65% reference level, an individualized decision should be made to hospitalize the patient for more aggressive therapy or to continue therapy at home with a course of prednisone.
- If PEF is < 40% reference level after repeated albuterol treatments, the patient should be admitted to the hospital unless, in the physician's best judgment, alternative treatment could suffice.

3) Prednisone Treatment:

In this protocol, prednisone will be used when acute exacerbations cannot be controlled by albuterol therapy. Indications for prednisone therapy may include the following:

- To achieve stable control of symptoms and optimize pulmonary function once treatment failure status is achieved.
- For follow-up management after discharge from the physician's office, emergency room, or hospital for an acute exacerbation.

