- An increase in "as needed" β -agonist use of ≥ 8 puffs per 24 hours over baseline use (baseline defined as average daily use over last 2 weeks of run-in period) for a period of 48 hours, or
- Use of ≥ 16 puffs of "as needed" β -agonist per 24 hours for a period of 48 hours.
- When PEF falls to $< 50\%$ reference level despite albuterol treatment.

The dose of prednisone used during an acute exacerbation shall consist of 60 mg as a single dose every day for 3 days, followed by a 10 mg/day taper over the next 5 days. The decision to initiate or to continue a course of prednisone beyond 8 days is left to the discretion of the physician.

C. Adjustment of Trial Medications During Asthma Exacerbations

Trial salmeterol or placebo will be continued during exacerbations which occur during the double-blind treatment period, unless the treating physician considers it appropriate to suspend such therapy until the exacerbation resolves. Reinstitution of trial medications (salmeterol or placebo) will occur when the exacerbation has resolved at the discretion of the investigator. Trial triamcinolone or placebo will be stopped during exacerbations, and open label triamcinolone acetate [400 μ g (4 puffs) BID] restarted unless the treating physician considers it appropriate to suspend such therapy until the exacerbation resolves. Reinstitution of open-label triamcinolone will occur when the exacerbation has resolved at the discretion of the investigator. A record of all medications, dosages, and frequency of occurrence will be kept during exacerbations. By definition, the development of a significant asthma exacerbation in SLIC constitutes treatment failure status.

Patients developing asthma exacerbation during the *run-in period* will be removed from the study. Once the exacerbation has been resolved, the patient may be considered for re-enrollment, starting again at Visit 1 and undergoing randomization into either SOCS or SLIC as previously described.

D. Study Center Visits Following Exacerbations

For safety reasons, all subjects will be seen within one week ($\pm 3d$) from the date of the exacerbation. Following this "safety" visit, subsequent protocol visits will continue in accordance with the visit schedule established at Visit 1 (see SOCS/SLIC MOP for details concerning possible replacement of scheduled protocol visits with treatment failure related visits).

E. Criteria for Discontinuing Patients Due to Asthma Exacerbations

1. Treatment Failure Status

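### After every treatment failure II.D, III.G.2 and V.E restore triamcinolone 800 µg/day, yet VI.A and VI.C let it be suspended in an exacerbation without requiring systemic corticosteroid

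*Protocol*

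**What the plan says.** Section VI.A states that "any patient who has developed a significant asthma exacerbation will also achieve treatment failure status"; III.F and VI.C agree.

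For treatment failure, III.G.2 says of patients that "their dose of inhaled corticosteroids will be increased to the dose they were receiving at visit 4", that is 800 µg/day, by open-label inhaler. V.E repeats this at each of Visits 5 to 10 and at the Treatment Failure Visit. The overview (II.D) says the same and places the increase alongside any steroid burst. In all these places the physician's exception concerns salmeterol only. The Treatment Failure Visit text goes on to state a hold for exacerbations, again for salmeterol alone: "Trial salmeterol will be continued during exacerbations unless the treating physician considers it appropriate to suspend such therapy until the exacerbation resolves". It then refers the reader onward: "see Section VI for additional information regarding the medical management of significant asthma exacerbations".

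Sections VI.A and VI.C stop blinded triamcinolone during an exacerbation and make open-label triamcinolone 400 µg BID the default, but qualify it: the drug is "restarted unless the treating physician considers it appropriate to suspend such therapy until the exacerbation resolves". Restart after resolution is left to the investigator.

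On systemic treatment, VI.B.3 says that "prednisone will be used when acute exacerbations cannot be controlled by albuterol therapy", followed by a list of indications worded as possibilities. For a patient whose PEF passes 65% of reference in the first hour of office or emergency care, VI.B.2 says: "Prednisone may be administered at the discretion of the physician to augment therapy".

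**The concern.** This trial deliberately withdraws inhaled corticosteroid, and the return to 800 µg/day is the protection it promises once a patient fails. A site following III.G.2 or V.E would give triamcinolone throughout an exacerbation. A site following VI.C might not. Under VI.C nothing requires another corticosteroid to be on board while triamcinolone is held, no maximum length is set, and resolution is not defined.

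At stake are patient safety and consistent handling after failure. Failed patients stay in follow-up under intent-to-treat, so uneven handling would also enter the post-failure secondary data, to an extent that cannot be sized.

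**Working it through.** No figure in the protocol has to be reproduced here. The check sets the sections side by side.

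| Place | Applies to | Inhaled corticosteroid | Exception for it |
|---|---|---|---|
| II.D | treatment failure | raised to 800 µg/day, concurrent with any burst | none |
| III.G.2 | treatment failure | raised to 800 µg/day, open label | none |
| V.E, Visits 5–10 and Treatment Failure Visit | treatment failure | same | none |
| VII.B.1 | exacerbation needing systemic corticosteroid | back to initial dose | none |
| VI.A, VI.C | significant exacerbation | open label, 400 µg BID | physician may suspend until resolution |

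**1. Same patients.** Every significant exacerbation is a treatment failure, so the first three rows and the last row apply to the same person. The treatment-failure rule without an exception stands in 1 (II.D) + 1 (III.G.2) + 6 (Visits 5–10) + 1 (Treatment Failure Visit) = 9 places. The suspension clause stands in 2.

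**2. Same default dose.** 400 µg × 2 = 800 µg/day, or 8 puffs of 100 µg. The sections differ only in the exception.

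**3. What is suspended.** Blinded triamcinolone is stopped in any case, and the sentence after the clause in VI.C names the open-label drug. A held patient therefore has no inhaled corticosteroid.

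**4. Is systemic corticosteroid guaranteed?** Take a patient whose PEF stays at or below 65% of reference, or whose symptoms do not improve, after 60 minutes of albuterol at home. VI.B.1 says: "This sequence of events constitutes a significant asthma exacerbation". In the office or emergency room, nebulized albuterol then brings PEF above 65% within the hour. The patient may go home, and prednisone is optional. If PEF stays below 65%, systemic treatment is to be considered. A significant exacerbation can also rest on symptoms plus heavy albuterol use (VI.A), which VI.B.3 lists only as a possible indication for prednisone. Several branches push strongly toward prednisone, but none is linked to the triamcinolone hold.

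**5. Dose change if both choices are made.** Group B goes from 800 to 0 µg/day. Groups A and C go from 800 to 0 before Visit 5, go from 400 to 0 in weeks 8–16, and stay at 0 after week 16. Under the masking in X.B, clinic staff cannot tell which applies.

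**6. Context for size.** Expected treatment failures at the rates in V.H and X.F:
- Group A: 0.50 × 20 = 10 to 0.60 × 20 = 12
- Group B: 0.05 × 65 = 3.25
- Group C: 0.20 × 65 = 13
- Total: 26.25 to 28.25 of 150

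This counts all failures. Significant exacerbations are a subset of unstated size, and uncovered holds are a subset of those.

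**The case against.** The best defence is that III.G.2 is the general rule and VI.C the specific one. III.G.2 sends patients who meet the Section VI criteria to its rescue algorithms, the Treatment Failure Visit text points to Section VI for managing exacerbations, and VI.C's default equals the III.G.2 dose. On that reading only short-term clinical discretion remains, and VI.B expressly leaves severe episodes to medical judgment. Prednisone is to be used when albuterol fails. A patient who goes home after a good first hour is responding to albuterol, and there is no evident reason to hold triamcinolone in such a patient. The hold is not unobserved either: the failure visit is preferred within 72 hours and a safety visit is due within one week ± 3 days.

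Much of this stands. VI.C can be read as the specific rule, and the uncovered state is remote. But the reading does not reconcile everything. The Treatment Failure Visit text itself states a hold for exacerbations and confines it to salmeterol, and II.D raises triamcinolone concurrently with a burst. Even with VI.C controlling, the hold carries no condition that another corticosteroid be given. The follow-up visits limit how long it could go unnoticed; they do not prevent it.

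**Conclusion.** The inconsistency is real and worth correcting as a low-frequency matter of safety and consistency. The text permits a patient in exacerbation to be on no corticosteroid, but only if triamcinolone is suspended and no systemic drug is given. Where prednisone is given, the hold leaves nobody uncovered.

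A reader might infer more, and the protocol does not support it:
- It does not direct anyone to leave a patient untreated; open-label 400 µg BID is the default in Section VI.
- The 26 to 28 expected failures are not the number at risk. The frequency of uncovered holds cannot be derived.
- The primary outcome is not biased. The failure has occurred before the clause operates.
- The hold is not open-ended in practice, since it runs to resolution and follow-up visits are required.

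The conclusion rests on the wording alone. It assumes that the manual of operations, which is not at hand, does not already settle the point.

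**What to change.** In VI.A and VI.C keep the instruction to stop blinded triamcinolone, and place the switch to open-label 400 µg BID at the Treatment Failure Visit or first Clinical Center contact, with blinded inhalers continued until then. The four inhalers issued at Visit 4 do not include open-label triamcinolone, so an earlier stop would leave nothing to switch to. Then choose one of two options.

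**Option 1, restrict the hold.** Replace the suspension clause and the restart sentence after it with: *Open-label triamcinolone may be withheld only while the patient is receiving oral or parenteral corticosteroid, and restarts no later than the day after the last such dose.* Add *except as allowed in VI.C* to the inhaled corticosteroid sentence in II.D, III.G.2, the seven V.E paragraphs and VII.B.1. II.D must be included, because it calls for the increase during the very burst in which this option allows a hold. With the standard prednisone course (3 days at 60 mg + 5-day taper = 8 days), the hold lasts at most 8 days, all covered.

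**Option 2, remove the hold.** Delete the triamcinolone suspension clause and its restart sentence from VI.A and VI.C. All sections then agree on the dose without further edits.

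Leave the salmeterol rules as they are. Option 1 costs two replaced clauses, ten short phrases and a site memo; option 2 costs two deletions and a memo. No new visit is needed. Both reduce physician discretion slightly. Option 1 may add a few prednisone courses, which feed the VI.F outcome of exacerbations defined by prednisone use, and the memo should say so. Neither option makes prednisone mandatory, and a Group A or C patient after week 16 stays on placebo triamcinolone until the visit.
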